7.2 Summary of Treatment Visits

7.2.1 Screening

The Screening visit must be performed within 28 days of Visit 1/Baseline. Subject informed consent must be obtained prior to initiation of any study specified procedures. Subjects who are taking primidone at screening who are otherwise deemed eligible for participation and are willing to discontinue primidone will be allowed an additional 2 weeks of screening (a total of 6 weeks) to ensure safe primidone discontinuation. A central reviewer will confirm the TETRAS-related eligibility criteria prior to randomization. Screening results from all patients meeting the eligibility requirements will be further assessed by the sponsor medical personnel for final approval of suitability for inclusion in the study. Details of the eligibility review will be provided in the study Operations Manual. See [Table 3](#) for a detailed list of assessments to be performed.

7.2.2 Visit 1 (Day 1 - Baseline)

Subjects will return to the clinic within 28 days of screening (or 42 days in the case of those with extended screening due to discontinuation of primidone.) Following confirmation of continued eligibility and randomization, subjects will undergo safety and efficacy assessments as detailed in Table 3 and will then receive their first dose of study drug (4 mg of CX-8998 or placebo). Subjects will be followed for adverse events for at least 2 hours after dosing. Orthostatic VS and triplicate ECGs will be obtained 1 to 2 hours after dosing. The investigator or qualified designee will make the determination whether it is safe to release the subject from the clinic. Subjects will be instructed to take the second daily dose of study drug no closer than 10 hours and no later than 14 hours (every 12 hours \pm 2 hours) from the time of their first dose, and to continue taking 4 mg (or placebo) twice daily for the following week (see Administration details in [Section 4.3](#)).

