5.2 Central Reviewers

A central reviewer will review eligibility criteria for all subjects. The site will submit an eligibility checklist for evaluation of each subject. A central reader will score the screening TETRAS performance video to determine if the subject meets Inclusion Criteria 5 and 6 below. No subject may be enrolled, randomized or dosed with study drug prior to receipt of notification that the central reviewer and review process has deemed the subject eligible.

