6.4.2 Procedures for Replacing Subjects Who Withdraw/Discontinue Prematurely

Subjects who withdraw from the study or discontinue treatment prematurely will not be replaced.

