(dosing days) orthostatic BP and pulse rate will be measured before dosing (recumbent and standing) and approximately 1-2 hours after dosing (recumbent and standing) as convenient between other required visit procedures. During any visit, blood pressure and pulse rate are to be assessed at any time subjects appear faint or complain of dizziness or other symptoms suggestive of hypotension. Respiratory rate and temperature will be measured in the recumbent position and need only be measured one time (with the first set of BP/pulse measurements). (Section 10.1.4.)

8. Clinical chemistry, hematology, urinalysis and coagulation panel. See Section 10.1.5 for complete details. Screening labs need not be repeated at Visit 1 (Day 1) if Day 1 is \leq 7 days from the screening visit. A positive drug screen will result in exclusion from the study unless it is explained by use of an allowed prescription medication (Section 10.1.6).
9. A triplicate 12-lead ECG will be performed at Screening and End of Study. At Visits 1, 2, 3 and 4 triplicate ECG will be performed predose and approximately 1-2 hours after the dose as convenient between other required visit procedures. All ECGs should be performed after at least 10 minutes of recumbency. (Section 10.1.8)
10. Women of childbearing potential only. A positive urine pregnancy test will be confirmed via serum testing. (Section 10.1.6)
11. Serum FSH only as needed to determine menopausal status in females < 62 years old with history of ≥ 12 months of amenorrhea without another cause.
12. Execution of the TETRAS Performance subscale will be video recorded for assessment by the central reader. Assessment by the site rater should be performed during the videotaping session. At Visit 1, the TETRAS Performance subscale should be performed prior to administration of study drug in the clinic. At Visits 3 and 4, the TETRAS Performance subscale should be performed during a window of 1 to 3 hours after administration of study drug in the clinic. (Section 8.1.1)
13. The Kinesia ONE device will be worn in the clinic after execution of the TETRAS Performance subscale assessment and, at Visit 1, prior to administration of study drug in the clinic. (Section 8.2.1)

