10.1.7 Pregnancy Tests

A urine pregnancy test will be performed for all women of childbearing potential. See [Section 6.2](#), inclusion criterion #8 for the definition of women of childbearing potential.

Positive urine tests will be confirmed with a serum pregnancy test. Subjects may not enter the study if pregnant and must be immediately discontinued from dosing as soon as any positive pregnancy test is reported during study participation.

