11.4 Analysis Populations

The populations defined for analysis will include the intent-to-treat (ITT) population, safety population, and a pharmacokinetic population. Additional analysis populations may be defined to evaluate study results. Any additional analysis populations will be defined in the SAP.

- **Intent-To-Treat Population:** The ITT population will include all subjects who are randomized. The ITT population will be used for analyses of accountability, demographics, and efficacy. Subjects will be analyzed according to the treatment as randomized.
- **Safety Population:** The safety population will include all subjects who are randomized and receive at least one dose of randomized treatment. Subjects who receive treatment other than that intended will be analyzed according to the treatment received. The safety population will be the primary population for all analyses of safety data.
- **PK Population:** The PK population will consist of all subjects for whom PK samples were obtained, received study treatment, and for whom sufficient plasma concentrations are available.

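### Section 7.2.2 randomises before the Visit 1 pre-dose checks, so ineligibility first shown by a same-day result is found in a subject who is already in the ITT population

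*Protocol*

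**What the plan says.** All references are to the latest protocol version in the file.

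- **Order at Visit 1.** Section 7.2.2: "Following confirmation of continued eligibility and randomization, subjects will undergo safety and efficacy assessments as detailed in Table 3". The same sentence puts the first dose after those assessments.
- **What is assessed then.** Note 9 to Table 3 (section 7.1): "At Visits 1, 2, 3 and 4 triplicate ECG will be performed predose". Note 7 requires orthostatic blood pressure and pulse before dosing at Visit 1. On the natural reading of Table 3, the urine pregnancy test and the C-SSRS are also due at Visit 1. The eligibility-criteria row is marked at Screening only.
- **Rules these results touch.** Section 10.1.7: "Subjects may not enter the study if pregnant and must be immediately discontinued from dosing". In section 6.3, exclusion 15c sets limits on QTcF, PR interval and AV block, and exclusion 15i covers symptomatic orthostatic hypotension.
- **Checks already placed before randomisation.** Section 5.2: "No subject may be enrolled, randomized or dosed with study drug prior to receipt of notification" of central clearance. The tremor thresholds are settled there too: "A central reader will score the screening TETRAS performance video to determine if the subject meets Inclusion Criteria 5 and 6 below". Section 7.2.1 repeats the timing: "A central reviewer will confirm the TETRAS-related eligibility criteria prior to randomization". It also adds approval by the sponsor's medical staff.
- **Analysis and replacement.** Section 11.4: "The ITT population will include all subjects who are randomized", and that population is used for efficacy. Section 6.4.2: "Subjects who withdraw from the study or discontinue treatment prematurely will not be replaced".

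**The concern.** Continued eligibility is confirmed and the subject is randomised before the day's tests are run. Read literally, the confirmation cannot draw on the only fresh evidence the visit produces. It rests on screening data that may be four weeks old, or six weeks old for a subject who stopped primidone, plus whatever the site learns by asking.

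A woman whose Visit 1 pregnancy test is positive, or a subject whose pre-dose QTcF is over the limit, is therefore found after the IWRS has assigned a treatment. That subject counts in the efficacy population, will probably have no Day 28 TETRAS score, and is not replaced on withdrawal. Such missing data can be avoided at no cost by changing the order of steps within one visit. For pregnancy, the order also strains the entry rule, because a randomised subject has on any ordinary reading entered the study.

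**Working it through.** **1. Which Visit 1 results can newly show ineligibility?**

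| Visit 1 item | Rule | Can it newly disqualify on the day? |
|---|---|---|
| Urine pregnancy test | 10.1.7 | Yes (a positive is confirmed by serum test) |
| Pre-dose ECG: QTcF, PR, AV block | Exclusion 15c | Yes |
| Pre-dose ECG: bradycardia | Exclusion 15c(iv) | Not alone; needs a repeat ECG on another day |
| Orthostatic vital signs | Exclusion 15i | Yes, if symptomatic |
| C-SSRS | Exclusion 15g is tied to screening | No; a yes to ideation item 4 or 5 acts through the withdrawal rule in 6.4 |
| TETRAS video | Criteria 5 and 6 use the screening video | No |
| Kinesia ONE | No criterion uses it | No |

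The point rests on three items: the pregnancy test, the three ECG limits and symptomatic orthostatic hypotension.

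**2. The plan's own power figure.** Inputs from sections 11.3 and 11.5.1.1: difference 5.5, SD 7.5, two-sided alpha 0.05, 53 per group, at least 90% power. Section 11.3 names a two-sample t-test with a non-parametric adjustment, taken here as multiplying n by 3/π.

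- Noncentrality = 5.5 / (7.5 × √(2/n)). At n = 53 this is 3.775 on 104 degrees of freedom, and power is 96.2%.
- Adjusted: 53 × 3/π = 50.6 effective per group, and power is 95.5%.
- Requirement for 90%: 41 per group by the t-test; 41 × π/3 = 42.9, so 43 per group adjusted.

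The stated figure reproduces. The 53 leaves 53 − 43 = 10 per group, or 10/53 = 18.9%, for losses. Section 11.3 says the number also covers dropouts and exclusions for major deviations, without giving a rate.

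**3. Size of the effect.** The protocol gives no Visit 1 failure rate, so 2 to 5% is an assumption for scale only: 0.02 × 106 = 2.1 and 0.05 × 106 = 5.3 subjects in total, or about 1 to 3 per arm.

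If they contribute no data:

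| Lost per arm | Adjusted power |
|---|---|
| 0 | 95.5% |
| 1 | 95.1% |
| 2 | 94.8% |
| 3 | 94.4% |
| 5 | 93.5% |
| 10 | 90.7% |
| 11 | 90.0% |
| 12 | 89.3% |

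If instead they stay in the analysis with no drug effect, the expected difference shrinks to 5.5 × (1 − f):

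- f = 2%: 5.39 points, adjusted power 94.7%
- f = 5%: 5.225 points, adjusted power 93.5%

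On either treatment, power stays well above 90%. Visit 1 failures do draw on the same allowance as ordinary dropout; total losses of up to 11 per arm keep adjusted power at 90%.

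**The case against.** The strongest reply is that the sentence in section 7.2.2 contains its own check, since continued eligibility is confirmed before randomisation. Central clearance and sponsor approval also come first, and section 7.2.1 leaves details of the eligibility review to an Operations Manual that is not at hand. In practice a site might run the ECG and pregnancy test before calling the IWRS. This stands in part: anyone who fails the confirmation is never randomised and never enters ITT, so a reader should not infer that everyone found ineligible on Day 1 is in the efficacy population. It does not close the gap, because the section places the Table 3 assessments after randomisation, and a manual should not have to reverse the protocol's sequence.

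Three further inferences are tempting and not supported:

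- *That ineligible subjects are exposed to drug because of this order.* The assessments already precede the first dose, so their results can be acted on before dosing under either order.
- *That the comparison is biased.* Assignment is blinded, so these failures should not depend on arm. The cost is missing data and dilution.
- *That the trial loses its stated power.* The calculation above shows otherwise.

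It is also fair to say that counting all randomised subjects in ITT is sound practice, and that handling of missing data and further analysis populations is properly left to the SAP. Neither is criticised here.

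**Conclusion.** The point holds in a narrow form. Section 7.2.2 randomises before the Visit 1 pre-dose assessments. A positive pregnancy test, a QTcF, PR or AV-block finding, or symptomatic orthostatic hypotension first seen that day therefore turns up in a subject already in the ITT efficacy population. Such a subject is not replaced on withdrawal and, for pregnancy, the order is in tension with the entry rule in section 10.1.7.

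The number affected is unknown and probably small: about 2 to 5 of 106 under the assumed 2 to 5%. If these were the only losses, adjusted power would be about 94 to 95% (93.5% if 5% stayed in with no effect), against the stated minimum of 90%. The conclusion assumes that the pregnancy test is due at Visit 1, as Table 3 appears to show, and that the order in 7.2.2 is followed as written. Severity: minor. It is worth correcting because the remedy costs almost nothing.

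**What to change.** Reword section 7.2.2 so that Visit 1 runs in this order:

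1. Complete and review the pre-dose procedures with same-day results: urine pregnancy test, triplicate ECG, orthostatic vital signs and C-SSRS. State that this review is the confirmation of continued eligibility.
2. Randomise in the IWRS.
3. Give the first dose.

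The C-SSRS belongs in step 1 because a Visit 1 answer can trigger withdrawal from treatment under section 6.4, although the exclusion score itself is tied to screening. The baseline TETRAS video and Kinesia ONE recording may also be made before randomisation, so that each randomised subject has a baseline for the ANCOVA. They should not be described as part of the eligibility decision.

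Cost: a short rewording, with the IWRS call made later in the same visit. No procedure or patient is added, and no sample-size input changes.

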7.2.3 Visit 2 (Day 8 – End of Week 1)

Subjects will return to the clinic for assessments as detailed in Table 3. Subjects will have withheld their morning dose of study drug.

If the subject has been at least 75% compliant with the study drug regimen (as detailed in [Section 4.4](#)) and has not experienced any intolerable adverse events (as described in [Section 4.5](#)), the dose of study drug will be increased to 8 mg (or placebo) twice daily for the following week. If compliance is determined to be less than 75%, up-titration should be discussed with the study safety representative.

Subjects will receive the first 8 mg dose of study drug (or placebo) and will then undergo safety assessments. Subjects will be followed for adverse events for at least 2 hours prior to discharge. Orthostatic VS and triplicate ECGs will be obtained 1 to 2 hours after dosing. The investigator or qualified designee will make the determination whether it is safe to release the subject from the clinic. Subjects will be instructed to take the second daily dose of study drug no closer than 10 hours and no later than 14 hours (every 12 hours \pm 2 hours) from the time of their first dose, and to continue taking 8 mg (or placebo) twice daily for the following week (see Administration details in [Section 4.3](#)).

7.2.4 Visit 3 (Day 15 – End of Week 2)

Subjects will return to the clinic for assessments as detailed in Table 3. Subjects will have withheld their morning dose of study drug.

If the subject has been at least 75% compliant with the study drug regimen (as detailed in [Section 4.4](#)) and has not experienced any intolerable adverse events (as described in [Section 4.5](#)), the dose of study drug will be increased to 10 mg (or placebo) twice daily for the following two weeks. If compliance is determined to be less than 75%, up-titration should be discussed with the study safety representative.

Subjects will receive the first 10 mg dose of study drug (or placebo) and will then undergo efficacy assessments between 1 and 3 hours after dosing. Subjects will be followed for adverse events for at least 2 hours prior to discharge. Orthostatic VS and triplicate ECGs will be obtained 1 to 2 hours after dosing. The investigator or qualified designee will make the determination whether it is safe to release the subject from the clinic. Subjects will be instructed to take the second daily dose of study drug no closer than 10 hours and no later than 14 hours (every 12 hours \pm 2 hours) from the time of their first dose, and to continue taking 10 mg (or placebo) twice daily for the following two weeks (see Administration details in [Section 4.3](#)).

7.2.5 Visit 4 (Day 28 – End of Week 4)

Subjects will return to the clinic for assessments as detailed in Table 3. Visit 4 is the end-of-dosing visit. Subjects will have withheld their morning dose of study drug. Subjects will receive the final dose of study drug (10 mg or placebo) and will then undergo efficacy assessments between 1 and 3 hours after dosing. Subjects will be followed for adverse events for at least 2 hours prior to discharge. Orthostatic VS and triplicate ECGs will be obtained 1 to 2 hours after dosing.

Visit must occur on or one day before Day 28 to ensure that all efficacy assessments occur while subject is still taking study drug.

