discontinuation. At Baseline, subjects will undergo safety and tremor assessments prior to dosing, will receive their first dose of study drug and will be monitored for safety for one hour following dosing. For one week, subjects will receive 4 mg (or matching placebo) twice daily. Subjects will return to the clinic on Day 8 for safety monitoring and dose up-titration to 8 mg (or matching placebo) twice daily. At Day 15 (Week 3) subjects will return to clinic for safety and efficacy assessments and final dose up-titration to 10 mg (or matching placebo) twice daily. The final efficacy visit will occur at Day 28 (Week 4). A final safety visit will occur at Day 35 (Week 5). Should subjects experience intolerable adverse events (AEs) at 4 mg BID, 8 mg BID or 10 mg BID, the dose may be decreased at Day 8 or Day 15 to the next lowest dose one time (or 2 mg BID in the case of the 4 mg BID dose). A dose reduction may be made if necessary prior to scheduled visits at Day 8 or Day 15. Re-up-titration is not allowed. Subjects not tolerating the next lowest dose or not tolerating 2 mg BID will be withdrawn from treatment. The study safety representative should be notified as soon as is feasible when a dose reduction is made.

Study Population:***Inclusion Criteria***

1. Signed informed consent form (ICF) indicating that the subject has been informed of the procedures to be followed, the experimental nature of the therapy, alternatives, potential benefits, side effects, risks, and discomforts.
2. Men or non-pregnant, non-breastfeeding women 18 to 75 years-of-age who are able to read and understand English.
3. Diagnosis of definite or probable bilateral essential tremor (ET) as defined by the Tremor Investigational Group with involvement of the hands and arms without present causes of enhanced physiologic tremor (Deuschl et al., 1998)
4. Diagnosis of ET before the age of 65
5. Tremor severity score of at least 2 in at least one upper extremity on at least one of the three maneuvers on the TETRAS scale
6. Total TETRAS performance score of at least 15. Note: Inclusion thresholds, including thresholds for items 5 & 6, should not be shared with study subjects or caregivers to limit Baseline inflation.

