4.3 Administration

CX-8998 (or placebo) will be administered as 4 mg (2 capsules) twice daily (8 mg/d) in the first week; increasing to 8 mg (4 capsules) BID (16 mg/d) in week 2, to a target of 10 mg (5 capsules) BID (20 mg/d) in weeks 3 and 4.

Treatment compliance will be assessed based on return of unused drug.

Subjects experiencing specified adverse events will have their dose adjusted. See [Section 4.5](#) for details on dose adjustments.

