4.5 Dose Adjustments / Toxicity Management

Adverse events will be graded for intensity by the investigator (see [Section 10.2.2.2](#)).

Dosing will be discontinued for all Grade 4 AEs.

In all subjects with intolerable AEs (as defined in [Section 10.2.1](#)) that are considered related to study drug, treatment should be suspended for up to 48 hours or until the AE resolves to a tolerable level of severity, whichever is earlier. Dosing may then be resumed at a previously tolerated lower dose (or 2 mg BID in the case of 4 mg BID). Only a single dose-step reduction (e.g. 10 mg BID to 8 mg BID, 8 mg BID to 4 mg BID, or 4 mg BID to 2 mg BID) is permitted. Re-up-titration is NOT permitted. Dosing should be discontinued if there is recurrence of intolerable AEs after dose reduction. Subjects on the 2 mg BID dose with intolerable AEs will be discontinued from treatment. Table 2 details dose reductions by dose level.

All subjects who discontinue treatment due to AEs will be followed for AE outcome. All AEs should be followed for resolution or for 30 days from the last dose of study drug, whichever is shorter.

Table 2: Study Drug Dose Reduction for Intolerable AEs

Dose and Schedule of Study Drug	Dose Reduction
2 mg BID	Remove from treatment ¹
4 mg BID	2 mg BID
8 mg BID	4 mg BID
10 mg BID	8 mg BID

1 – Subjects who are removed from treatment for AE(s) should be followed for resolution of the AE(s) and should complete all assessments scheduled for the EOS/FU Visit as well as all assessments that they are capable of completing on the Visit day if the decision to remove from treatment is made on a Visit day. Likewise, if the investigator plans to temporarily interrupt dosing because of an AE and the decision is made on a visit day, then the subject should complete all scheduled assessments that they are capable of completing on the visit day they appear.

The study safety representative should be notified of all dose reductions as soon as is feasible.

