25. AEs will be collected from signature of the ICF through 30 days after the last dose of study drug [\(Section 10.2.2\)](#). Adverse events will be followed for resolution in accordance with [Section 10.2.3](#).
26. The first dose of study drug at each dose level will be administered in the clinic. Subjects will be instructed to eat breakfast. At Visits 2, 3, and 4 subjects should hold their morning dose, as their dose will be administered in the clinic after the subject has undergone the first set of orthostatic VS and required pre-dose PK sampling, and/or has been evaluated by the investigator for suitability to undergo specified dose increase. Subjects will remain under observation for a minimum of 2 hours post dosing prior to discharge at Visits 1, 2 and 3, or the time that is required to complete all of the required procedures for the visit [\(Section 4.3\)](#).
27. Subjects will initiate dosing at 4 mg (2 capsules) administered twice daily with food. After 7 days dosing, the dose will be increased to 8 mg (4 capsules) twice daily, per subject tolerance. After 7 days at 8 mg BID, the dose will be increased to 10 mg (5 capsules) twice daily, per subject tolerance (Section 4.3.).
28. Compliance will be assessed via pill counts. [\(Section 4.4.\)](#)

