10.4 Safety Monitoring and Risk Mitigation Plan

Measures to minimize the risks to subjects enrolled in this clinical trial have been taken with respect to the following study design elements:

1. Subject safety and tolerability will be monitored in this study across multiple dimensions by tracking clinical adverse events; vital signs (including orthostatic pulse and blood pressure); general and neurological physical examinations; standard clinical laboratory safety panels for complete blood counts, chemistry, coagulation, and urinalysis; standard 12-lead electrocardiograms; and the Epworth Sleepiness Scale (ESS) and Columbia Suicide Severity Rating Scale (C-SSRS).
2. The specified inclusion/exclusion criteria have been carefully considered to avoid enrollment of subjects for whom exposure to the study drug might pose a hazard.
3. The anticipated subject population (with essential tremor) is acknowledged to likely be older than the healthy volunteer and schizophrenic populations that have previously undergone phase 1 and 2 study with CX-8998 (formerly MK-8998, Merck & Co, Inc). Since older male and female subjects may experience greater CX-8998 exposures than younger males on whom most of the existing PK data are based, this study will perform a careful dose titration in which dosing of CX-8998 will be initiated at 4 mg BID for 7 days, increasing to 8 mg BID for 7 days, and finally, if tolerated, to the target dose of 10 mg BID for 14 days. Subjects will return to the clinic for each dose up-titration for safety assessment. The study is designed to allow for flexible titration; should subjects experience intolerable AEs (see

[Section 10.2.1, Adverse Events, Definitions](#)) at 4 mg, 8 mg or 10 mg BID, the dose may be decreased to the previous lower dose (2 mg BID in the case of 4 mg BID). Subjects experiencing intolerable AEs at 2 mg BID will be discontinued from treatment.

4. Dose up-titration (e.g., from 4 mg BID to 8 mg BID) requires that the subject be evaluated in the clinic by the PI or sub-I. PI's and sub-I's may advise a subject to reduce or suspend their dose based on telephone elicitation of adverse events. During each clinic visit involving a dose up-titration, subjects will be observed and monitored in the clinic for at least 2 hours following the first administration of the increased dose step.

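### Section 7.2.5 gives the Visit 4 clinic dose as 10 mg for everyone, which is misstated for subjects whose dose was reduced under Section 4.5

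*Protocol*

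**What the plan says.** Section 7.2.5 has subjects come to Visit 4 without having taken their morning dose, and continues: "Subjects will receive the final dose of study drug (10 mg or placebo) and will then undergo efficacy assessments", with those assessments 1 to 3 hours after dosing. The milligram amount carries no tolerance condition and no reference to Section 4.5.

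Section 4.5 and Table 2 allow one reduction step for an intolerable adverse event related to study drug: 10 to 8, 8 to 4, or 4 to 2 mg BID. The subject may then stay on treatment at the lower dose. The section adds: "Re-up-titration is NOT permitted". The study design part of the synopsis repeats the rule: "Re-up-titration is not allowed".

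Several other places bear on what was intended:

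- Section 4.3 sets out the 4, 8 and 10 mg schedule with 10 mg as a target, and refers to Section 4.5 for subjects whose dose is adjusted because of adverse events.
- Note 26 to Table 3 covers in-clinic dosing at Visits 2, 3 and 4. It has subjects hold the morning dose because that dose, their own, is given at the clinic.
- Note 27 to Table 3: "the dose will be increased to 10 mg (5 capsules) twice daily, per subject tolerance".
- Section 10.4, item 3: "finally, if tolerated, to the target dose of 10 mg BID for 14 days".
- Section 10.4, item 4, says that an up-titration "requires that the subject be evaluated in the clinic by the PI or sub-I".
- Section 7.2.4 (Visit 3) allows the increase to 10 mg only if the subject is at least 75% compliant and "has not experienced any intolerable adverse events".

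**The concern.** A subject whose dose was reduced reaches Day 28 on 8, 4 or 2 mg BID. For that subject the dose printed in Section 7.2.5 is a step up after a reduction, which Section 4.5 and the synopsis rule out. A coordinator working from the visit section sees an explicit milligram figure and nothing to say that it does not apply to everyone.

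The timing makes the sentence worth correcting. The Visit 4 dose comes 1 to 3 hours before the TETRAS Performance assessment that supplies the primary endpoint, and 1 to 2 hours before the ECGs and orthostatic measurements. It also comes 4 to 6 hours before the post-dose PK sample, and Section 9.2 summarises concentrations by visit and dose. If the sentence were followed literally, the error would be in the unsafe direction, and a reduced subject's Day 28 data would follow a dose that the subject was not otherwise taking. Only the CX-8998 arm would see a change in drug exposure.

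**Working it through.** No statistical figure is involved. The check compares the dosing rules and does simple arithmetic on the dose steps.

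**Inputs.** Capsules are 2 mg (Section 4.1). The reduction steps are 10 to 8, 8 to 4 and 4 to 2 mg BID (Section 4.5, Table 2). The stated Visit 4 dose is 10 mg (Section 7.2.5).

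**Step 1: can a subject be below 10 mg at Day 28?** Yes. Section 4.5 permits dosing to resume at the lower level and bars a later increase, so a reduced subject who remains on treatment takes 8, 4 or 2 mg BID until Day 28.

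**Step 2: what would the literal text do?** The excess is 10 minus the current dose. Extra capsules are that excess divided by 2. The ratios are 10 divided by the current dose, and 10 divided by the dose that was not tolerated.

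| Reduction | Current dose | Excess | Extra capsules | Ratio to current dose | Ratio to dose not tolerated |
|---|---|---|---|---|---|
| 10 to 8 mg | 8 mg | 10 − 8 = 2 mg | 1 | 10/8 = 1.25 | 10/10 = 1.0 |
| 8 to 4 mg | 4 mg | 10 − 4 = 6 mg | 3 | 10/4 = 2.5 | 10/8 = 1.25 |
| 4 to 2 mg | 2 mg | 10 − 2 = 8 mg | 4 | 10/2 = 5 | 10/4 = 2.5 |

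In each row the literal dose is at or above the level that the subject failed to tolerate.

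**Step 3: does the rest of the protocol settle the meaning?** It does. Section 4.3 makes Section 4.5 the exception to the planned schedule. Note 26 has the clinic give the subject's own held dose at Visit 4, which for a reduced subject is 8, 4 or 2 mg. Note 27 and Section 10.4 tie 10 mg to tolerance. Increases are scheduled only at Days 8 and 15, so Visit 4 contains no titration decision. Read as a whole, the protocol calls for the current dose, and only the wording of Section 7.2.5 is out of line.

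**Step 4: who is covered?** Only dose-reduced subjects. A subject who stayed below 10 mg for another reason, such as poor compliance, has had no reduction, so the ban does not strictly apply. For that subject Section 7.2.5 merely fails to match the evident intent.

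**The case against.** The best reply is that Section 7.2 summarises visits along the planned path, so 10 mg in Section 7.2.5 is simply the nominal dose. The dose sentences in Sections 7.2.3 and 7.2.4 are equally bare; the tolerance condition there attaches to the decision to increase, and Visit 4 has no such decision. Section 4.3 already sends adverse-event dose changes to Section 4.5, note 26 already gives the right answer for the clinic dose, and the ban appears in two places. For harm to follow, a site would have to override an explicit and repeated prohibition because of a parenthesis.

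Most of this stands. It disposes of a stronger inference that a reader might draw, namely that Sections 7.2.5 and 4.5 cannot both be followed and that sites are left with no rule to choose between them. The protocol does supply the rule. The reply also weakens any sharp contrast between Visit 4 and Visits 2 and 3.

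It does not make the sentence right. Section 7.2.5 does more than omit a qualifier: it states a specific amount for all subjects, and that amount is incorrect for a group that the protocol itself creates. The reader has to go to other sections to find this out.

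**Conclusion.** The point holds as a minor local misstatement. Section 7.2.5 gives the wrong Visit 4 dose for subjects reduced to 8, 4 or 2 mg BID, while the rest of the protocol makes the current dose the intended one and puts Section 4.5 in charge.

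The size is at most one dose per reduced subject, with the ratios shown above, and those arise only if a site follows the sentence literally. The protocol gives no dose-reduction rate, so the number of subjects concerned cannot be estimated. Practical risk is low because the ban is stated twice, Section 10.4 requires an investigator or sub-investigator to evaluate the subject before any up-titration, and none is scheduled at Visit 4. Sample size, power and alpha do not change.

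A reader might also infer that the Day 28 efficacy comparison is compromised. The protocol does not support that: nothing in it indicates that sites would dose against Section 4.5.

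**What to change.** Reword the dose sentence in Section 7.2.5 along these lines: *Subjects will receive the final dose of study drug at their current dose level (up to 10 mg, or placebo; no re-up-titration, see Section 4.5)*, leaving the 1 to 3 hour assessment window as it is. This also covers subjects who never reached 10 mg for reasons other than a reduction.

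A matching qualifier such as *if up-titrated* in the dose sentences of Sections 7.2.3 and 7.2.4 would be consistent but is optional, since both sections already make the increase conditional on Section 4.5. The cost is one phrase. No procedure, visit or analysis changes.
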